## Injection Procedures (PFS)

### 1. Setting up for an injection

- Find a clean flat surface.
- Do not use if the seals on the carton are broken or missing. Contact your study doctor's office if the seals are broken.
- Take one kit with the prefilled syringe(s) of adalimumab from the refrigerator. Do not use a prefilled syringe that has been frozen or if it has been left in direct sunlight.
- Return any unused syringe(s) to the refrigerator.

You will need the following items for each dose:

- study medication in pre-filled syringe(s)
- alcohol prep(s)
- cotton ball or gauze pad(s)

[figure not shown]

If you do not have all of the items you need to give yourself an injection, call your study physician. Use only the items provided in the box your adalimumab comes in.

- Make sure the liquid in the prefilled syringe is clear and colorless. Do not use a prefilled syringe if the liquid is cloudy or discolored or has flakes or particles in it.
- Have a special sharps (puncture proof) container nearby for disposing of used needles and syringes.

For your protection, it is important that you follow these instructions.

## 2. Choosing and preparing an injection site

- Wash your hands well.
- Choose a site on the front of your thighs or your stomach area (abdomen). If you choose your abdomen, you should avoid the area 2 inches around your belly button (navel).
- Choose a different site each time you give yourself an injection. Each new injection should be given at least one inch from a site you used before. Never inject into areas where the skin is tender, bruised, red or hard or where you have scars or stretch marks.
- If you have psoriasis, you should try not to inject directly into any raised, thick, red or scaly skin patches or lesions.

[figure not shown]
- You may find it helpful to keep notes on the location of your injection sites.
- Wipe the site where adalimumab is to be injected with an alcohol prep (swab), using a circular motion. Do not touch this area again until you are ready to inject.

### **3. How to prepare your adalimumab dose for injection with a Prefilled Syringe**

- Hold the syringe upright with the needle facing down. Check to make sure that the amount of liquid in the syringe is the same or close to the 0.8 mL line for the 40 mg prefilled syringe. The top of the liquid may be curved. If the syringe does not have the correct amount of liquid, do not use that syringe. Call your study doctor.
- Remove the needle cover taking care not to touch the needle with your fingers or allow it to touch any surface.
- Turn the syringe so the needle is facing up and slowly push the plunger in to push the air in the syringe out through the needle. If a small drop of liquid comes out of the needle that is okay.
- Do not shake the syringe.

#### 4. Injecting Adalimumab

- With your other hand, gently squeeze an area of the cleaned area of skin and hold it firmly.
- You will inject into this raised area of skin. Hold the syringe like a pencil at about a 45° angle (see picture) to the skin.
- With a quick, short, "dart-like" motion, push the needle into the skin.
- After the needle is in, let go of the skin. Pull back slightly on the plunger. If blood appears in the syringe it means that you have entered a blood vessel. Do not inject adalimumab. Pull the needle out of the skin and repeat the steps to choose and clean a new injection site. Do not use the same syringe. Dispose of it in your special sharps container. If no blood appears, slowly push the plunger all the way in until all of the adalimumab is injected.
- When the syringe is empty, remove the needle from the skin keeping it at the same angle it was when it was pushed into the skin.
- Press a cotton ball or gauze pad over the injection site and hold it for 10 seconds. Do not rub the injection site. You may have slight bleeding. This is normal.
- Dispose of the syringe right away into your special sharps container.

**Appendix H. Crohn's Disease Activity Index (CDAI)**

			Factor	Subtotal
1. Number of liquid or very soft stools (Record the frequency per day)	$\frac{+}{\text{Days: 1}} + \frac{+}{2} + \frac{+}{3} + \frac{+}{4} + \frac{+}{5} + \frac{+}{6} + \frac{+}{7} = \frac{\quad}{\text{Sum}}$	×	2	
2. Abdominal pain rating: 0 = none, 1 = mild, 2 = moderate, 3 = severe	$\frac{+}{\text{Days: 1}} + \frac{+}{2} + \frac{+}{3} + \frac{+}{4} + \frac{+}{5} + \frac{+}{6} + \frac{+}{7} = \frac{\quad}{\text{Sum}}$	×	5	
3. General well-being: 0 = generally well, 1 = slightly underpar, 2 = poor, 3 = very poor, 4 = terrible	$\frac{+}{\text{Days: 1}} + \frac{+}{2} + \frac{+}{3} + \frac{+}{4} + \frac{+}{5} + \frac{+}{6} + \frac{+}{7} = \frac{\quad}{\text{Sum}}$	×	7	
4. Number of 6 listed categories the subject now has Check all items that apply:  Arthritis/arthralgia  Iritis/uveitis  Erythema nodosum/pyoderma gangrenosum/aphthous stomatitis  Fissure, abscess and/or anal fistula (draining/non-draining)  Other cutaneous fistula (draining/non-draining) Fistula  Fever over 100°F (37.8°C) during past week	_____ _____  Record "0" if no categories checked	×	20	
5. Taking Lomotil/Imodium/ Loperamide/opiates for diarrhea 0 = no, 1 = yes	_____	×	30	
6. Abdominal mass 0 = none, 2 = questionable, 5 = defined	_____	×	10	
7. Hematocrit: ____.	Male: (47 – hematocrit) = Female: (42 – hematocrit) = Subtotal If hematocrit > normal, enter "0"	×	6	
8. Body weight: ____.(kg) Standard weight: ____.(kg)	$100 \times [1 - (\text{Body wt}/\text{Standard wt})] =$ Percent below standard weight: _____ If body wt > std. wt, enter "0"	×	1	
			Total	

**Appendix I. Standard Weights**

Standard Height and Weight Tables – Use to Calculate CDAI Score		
Standard Height cm (Inches)	Standard Weight (Men) kg (Pounds)	Standard Weight (Women) kg (Pounds)
121.9 (48.0)		40.8 (89.9)
123.2 (48.5)		41.3 (91.0)
124.5 (49.0)		41.8 (92.1)
125.7 (49.5)		42.3 (93.3)
127.0 (50.0)		42.8 (94.4)
128.3 (50.5)		43.4 (95.6)
129.5 (51.0)		43.9 (96.8)
130.8 (51.5)		44.4 (98.0)
132.1 (52.0)	55.5 (122.4)	45.0 (99.2)
133.4 (52.5)	55.7 (122.7)	45.5 (100.4)
134.6 (53.0)	55.8 (123.1)	46.1 (101.6)
135.9 (53.5)	56.0 (123.5)	46.6 (102.8)
137.2 (54.0)	56.2 (123.9)	47.2 (104.1)
138.4 (54.5)	56.4 (124.4)	47.8 (105.3)
139.7 (55.0)	56.7 (124.9)	48.3 (106.6)
141.0 (55.5)	56.9 (125.5)	48.9 (107.9)
142.2 (56.0)	57.2 (126.1)	49.5 (109.1)
143.5 (56.5)	57.4 (126.7)	50.1 (110.4)
144.8 (57.0)	57.7 (127.3)	50.7 (111.7)
146.1 (57.5)	58.1 (128.0)	51.3 (113.0)
147.3 (58.0)	58.4 (128.7)	52.2 (115.0)
148.6 (58.5)	58.7 (129.5)	52.6 (116.0)
149.9 (59.0)	59.1 (130.3)	53.1 (117.0)
151.1 (59.5)	59.5 (131.1)	53.6 (118.3)
152.4 (60.0)	59.9 (132.0)	54.2 (119.5)
153.7 (60.5)	60.3 (132.9)	54.8 (120.8)
154.9 (61.0)	60.7 (133.8)	55.3 (122.0)
156.2 (61.5)	61.1 (134.8)	56.0 (123.5)
157.5 (62.0)	61.7 (136.0)	56.7 (125.0)

Standard Height and Weight Tables – Use to Calculate CDAI Score		
Standard Height cm (Inches)	Standard Weight (Men) kg (Pounds)	Standard Weight (Women) kg (Pounds)
158.8 (62.5)	62.1 (137.0)	57.4 (126.5)
160.0 (63.0)	62.6 (138.0)	58.0 (128.0)
161.3 (63.5)	63.0 (139.0)	58.7 (129.5)
162.6 (64.0)	63.5 (140.0)	59.4 (131.0)
163.8 (64.5)	64.1 (141.3)	60.1 (132.5)
165.1 (65.0)	64.6 (142.5)	60.8 (134.0)
166.4 (65.5)	65.2 (143.8)	61.4 (135.5)
167.6 (66.0)	65.8 (145.0)	62.1 (137.0)
168.9 (66.5)	66.4 (146.5)	62.8 (138.5)
170.2 (67.0)	67.1 (148.0)	63.5 (140.0)
171.5 (67.5)	67.8 (149.5)	64.2 (141.5)
172.7 (68.0)	68.5 (151.0)	64.9 (143.0)
174.0 (68.5)	69.2 (152.5)	65.5 (144.5)
175.3 (69.0)	69.8 (154.0)	66.2 (146.0)
176.5 (69.5)	70.5 (155.5)	66.9 (147.5)
177.8 (70.0)	71.2 (157.0)	67.6 (149.0)
179.1 (70.5)	71.9 (158.5)	68.3 (150.5)
180.3 (71.0)	72.6 (160.0)	68.9 (152.0)
181.6 (71.5)	73.4 (161.8)	69.6 (153.5)
182.9 (72.0)	74.1 (163.5)	70.3 (155.0)
184.2 (72.5)	75.0 (165.3)	71.2 (156.9)
185.4 (73.0)	75.7 (167.0)	71.9 (158.5)
186.7 (73.5)	76.6 (169.0)	72.6 (160.2)
188.0 (74.0)	77.5 (171.0)	73.4 (161.8)
189.2 (74.5)	78.4 (172.8)	74.1 (163.4)
190.5 (75.0)	79.1 (174.5)	74.9 (165.1)
191.8 (75.5)	80.2 (176.8)	75.6 (166.8)
193.0 (76.0)	81.2 (179.0)	76.4 (168.4)
194.3 (76.5)	82.0 (180.8)	77.2 (170.1)
195.6 (77.0)	82.9 (182.9)	77.9 (171.8)
196.9 (77.5)	83.9 (185.0)	78.7 (173.5)

Standard Height and Weight Tables – Use to Calculate CDAI Score		
Standard Height cm (Inches)	Standard Weight (Men) kg (Pounds)	Standard Weight (Women) kg (Pounds)
198.1 (78.0)	84.9 (187.2)	79.5 (175.2)
199.4 (78.5)	85.9 (189.4)	80.3 (177.0)
200.7 (79.0)	86.9 (191.6)	81.0 (178.7)
201.9 (79.5)	87.9 (193.9)	81.8 (180.5)
203.2 (80.0)	89.0 (196.2)	82.6 (182.2)
204.5 (80.5)	90.0 (198.6)	*Standard height is calculated using actual height obtained at screening (without shoes) plus one inch
205.7 (81.0)	91.1 (200.9)	*Indoor clothing weighing 5 pounds for men and 3 pounds for women
207.0 (81.5)	92.2 (203.3)	*Centimeters × 0.3937 = inches
208.3 (82.0)	93.3 (205.8)	*Pounds × 0.4535 = kilograms

**Appendix J. 70-Day Follow-Up Phone Call – Sample**

Site Name/Number: \_\_\_\_\_

Subject Number: \_\_\_\_\_

**Please contact subjects that discontinue adalimumab 70 days following study drug discontinuation.**

Date of Call: \_\_\_\_\_

- Lost to Follow-up (Please check this box if subject was not willing to provide any follow-up information or you were unable to speak to the subject following at least one attempt.)
- No Events Reported
- N/A subject continued adalimumab therapy after the end of their study participation or moved into the OLE study (M14-347).

**List any Adverse Events (AE) and/or Serious Adverse Events (SAE) that occurred since the subject was last seen in clinic for this study. If needed, provide AE/SAE details on the AE worksheet attached. (Please report all SAEs to AbbVie within 24 hours of being made aware of the event.)**

---

---

---

---

---

If events are listed above, your monitor will review and retrieve the appropriate eCRF pages during their next visit.

Please fax all completed forms to:

[Name] at XXX-XXX-XXXX

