**Table 2. Adalimumab Dose Adjustment Criteria**

[figure not shown]
Adalimumab Dose Adjustment Criteriaa			
ADA Serum Concentrationb (ug/mL)	CDAIc	hs-CRPd (mg/L)	Dose Change?
Clinically Adjusted Regimen			
any	< 220	< 10	no
any	any	≥ 10	yes; dose escalate to ew
any	≥ 220	any	yes; dose escalate to ew
Therapeutic Drug Monitoring Regimen			
< 5	any	any	yes; dose escalate to ew
5 – 10	< 220	< 10	no
5 – 10	any	≥ 10	yes; dose escalate to ew
5 – 10	≥ 220	any	yes; dose escalate to ew
> 10	any	any	no

- For subjects experiencing an active infection or those for whom the investigator feels dose escalation is not advisable, the investigator should contact the Study Designated Physician.
- Measured from the serum concentration taken at the prior study visit.
- Measured using hematocrit taken from prior study visit for CDAI calculation.
- Measure using hs-CRP from the prior or current study visit.

The duration of the study could be up to 60 weeks which includes a Screening Period (1 – 4 weeks, ± 3 days which is granted around all study visits), a 12 week double-blind period Induction Study, and a double-blind 44-week Maintenance Study. The Screening Period may be extended as necessary after consultation and approval with the AbbVie Study Designated Physician (SDP) for subjects who require initiation of prophylactic anti-tuberculosis (TB) therapy, or in case of external, not subject-related circumstances (e.g., due to delay of availability of screening test results). There will also be a 70-day follow-up phone call for subjects who complete Week 56 or discontinue from the study prematurely.

A schematic of the study design is presented in [Figure 2](#).

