A final phone call will be made to the subject approximately 70 days after the last dose of study drug to determine the status of any ongoing AEs/SAEs or the occurrence of any new AEs/SAEs. The 70-day follow-up phone call will not be required for any subject that initiates commercial adalimumab.

All attempts must be made to determine the date of the last dose of study drug and the primary reason for premature discontinuation. The information will be recorded on the appropriate eCRF page.

For subjects that are considered lost to follow-up, reasonable attempts must be made to obtain information on the final status of the subject. At a minimum, two phone calls must be made and one certified letter must be sent.

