### 6.1.4 Adverse Event Collection Period

All adverse events reported from the time of study drug administration until 70 days following discontinuation of study drug administration have elapsed will be collected, whether solicited or spontaneously reported by the subject. In addition, serious adverse events will be collected from the time the subject signed the study-specific informed consent. Adverse event information will be collected and recorded on the appropriate eCRFs.

[figure not shown]
Subjects will be contacted approximately 70 days following study drug discontinuation for an assessment of any new or ongoing AEs, except those subjects that continue on adalimumab therapy after the end of study participation. These subjects are not required to complete the 70-day follow-up and any new Adverse Events should be reported

through the mechanism used for all post-marketing adverse experiences. The 70-day follow-up phone call will be recorded in source document only and confirmation of the contact will be faxed to AbbVie ([Appendix J](#)).

All Adverse Events identified to AbbVie from the 70-day follow-up phone call will be collected as source data to be evaluated and reported ([Figure 3](#)). Thus, all SAEs and nonserious AEs as defined by AbbVie, reported during the 70-day follow-up phone call must be captured in the clinical database. The end of trial is the last subject contact, i.e., the 70-day follow-up call.

Adverse event information will be collected as shown in [Figure 3](#).

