11.2 Analysis of Adverse Events

11.2.1 Treatment-Emergent Adverse Events

Treatment-emergent AEs during Maintenance Study are defined as events that begin or worsen either on or after the first dose of the study drug and within 70 days after the last dose of the study drug.

The 70-day follow-up phone call will not be required for any subject that initiates commercial adalimumab.

An overview of treatment-emergent AEs, including AEs of special interest such as adverse events leading to death and adverse events leading to premature discontinuation, AEs by Medical Dictionary for Drug Regulatory Activities (MedDRA version 21.0 or later) preferred term and system organ class, AEs by maximum relationship to study drug, and AEs by maximum severity will be summarized by number and percent.

The number and percent of subjects experiencing treatment-emergent adverse events will be summarized for the following adverse event categories.

- Any treatment-emergent adverse event.
- Any treatment-emergent adverse event that was rated as possibly related to study drug by the investigator (Reasonable Possibility).
- Any treatment-emergent severe adverse event.
- Any treatment-emergent serious adverse event.
- Any treatment-emergent adverse event leading to discontinuation of study drug.
- Any treatment-emergent adverse event leading to death.
- Any treatment-emergent adverse event of special interest.
- Any Deaths

Treatment-emergent adverse events will be summarized as follows:

- Grouped by System Organ Class and Preferred Term.
- A by-subject listing will be provided.
- Grouped by System Organ Class, Preferred Term and Severity.
- Grouped by System Organ Class, Preferred Term and Relationship to Study Drug.
- Grouped by System Organ Class and Preferred Term with subject numbers.

In treatment-emergent AE tables, a subject who reports more than one treatment-emergent AE in different system organ classes will be counted only once in the overall total. A subject who reports two or more different preferred terms which are in the same SOC will be counted only once in the SOC total. A subject who reports more than one treatment AE with the same preferred term will be counted only once for that preferred term using the most extreme incident (i.e., most "severe" for the severity tables and most "related" for the relationship tables).

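### The Appendix J form for the 70-day safety call accepts one failed attempt as lost to follow-up, while Section 5.4.1 asks for two calls and a certified letter

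*Protocol*

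**What the plan says.** Section 5.4.1 of the protocol describes the contact: "A final phone call will be made to the subject approximately 70 days after the last dose of study drug". Its purpose is to learn of ongoing and new adverse events. The same section then turns to subjects who cannot be reached: "For subjects that are considered lost to follow-up, reasonable attempts must be made to obtain information on the final status of the subject". It adds the minimum effort: "At a minimum, two phone calls must be made and one certified letter must be sent".

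Appendix J is the sample form for that call. Its Lost to Follow-up box is to be checked if the subject would not give information, or if "you were unable to speak to the subject following at least one attempt". It mentions neither a second call nor a letter. Section 6.1.4 says that the call is recorded in source documents only and that confirmation of contact is faxed to the sponsor, and it cites Appendix J.

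The window that the call serves is defined in several places. Section 6.1.4 of the protocol states that adverse events reported from first dosing "until 70 days following discontinuation of study drug administration have elapsed will be collected". Section 11.2.1 of both SAPs counts events as treatment-emergent if they begin or worsen "within 70 days after the last dose of the study drug". The Induction SAP limits this to subjects who enter neither Maintenance nor the open-label extension. Section 5.1 of the protocol defines who is called; it provides for a "70-day follow-up phone call for subjects who complete Week 56 or discontinue from the study prematurely".

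**The concern.** The same status, lost to follow-up, carries two different minimum efforts, and the lower one is printed on the form in use when the call is made. A site that works from the form can check the box after one unanswered call and be consistent with what the form asks, while falling short of Section 5.4.1.

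What is at stake is the capture of adverse events between the last visit and the end of the 70-day window. No other contact is scheduled in that interval. An event there that is neither reported spontaneously nor asked about would not reach the treatment-emergent tables.

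**Working it through.** No power, alpha or event-rate calculation applies, and the plan states no figure to reproduce. The check is a comparison of current protocol text, followed by simple arithmetic on the window.

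**Step 1: the two minimums side by side.**

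| Item | Section 5.4.1 | Appendix J |
|---|---|---|
| Call attempts, minimum | 2 | 1 |
| Certified letters, minimum | 1 | 0 (none mentioned) |
| Status of the text | mandatory wording in the body | sample form, instruction for a check box |

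Shortfall of the form: 2 − 1 = 1 call, and 1 − 0 = 1 letter.

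**Step 2: what the sponsor sees.** The faxed form has a single line for the date of the call and no field for a second attempt or a letter. From the form alone the sponsor cannot tell whether the Section 5.4.1 minimum was met. The same box also combines refusal with failure to reach the subject.

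**Step 3: length of the interval that the call covers.** The window is 70 / 7 = 10 weeks from the last dose.

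- Early discontinuers: Section 5.4.1 places the discontinuation visit within 2 weeks of the last dose. The uncovered interval is 10 − 2 = 8 weeks to 10 − 0 = 10 weeks.
- Week 56 completers: Appendix G schedules the last home injection at Week 55, and no dose is given at Week 56. The window ends at 55 + 10 = Week 65, so 65 − 56 = 9 weeks remain after the final visit (nominal weeks, ignoring visit windows).

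**Step 4: who is affected.** In the Induction analysis, treatment-emergence ends at the first Maintenance or extension dose for those who continue. The Synopsis says that all Induction completers continue into Maintenance, so the interval matters essentially for early discontinuers. In the Maintenance analysis it applies to completers and discontinuers alike. Subjects who continue adalimumab after the study need no call.

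**Step 5: effect on the tables.** Section 11.2.1 of both SAPs gives rates as events per 100 patient-years of exposure. Under Section 9.0, exposure for Maintenance subjects and for Induction discontinuers is the last dose date minus the first dose date plus 14 days. That denominator is the same whether or not the call succeeds. A missed event therefore lowers the observed rate and cannot raise it. Section 8.0 of both SAPs lists no count of completed 70-day contacts, so the planned tables would not show how many intervals were left unobserved.

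**The case against.** The strongest reply is that the two texts can both be obeyed. The form's one attempt is a floor, the form is labelled a sample, and Section 5.4.1 is mandatory. A site that makes two calls and sends a letter satisfies both. This stands: the form permits less than the body requires, but it does not forbid more.

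A reader might infer that the form ends follow-up once the box is checked. The documents do not say so. Appendix J says only when to check the box. Read literally, Section 5.4.1 asks for the calls and the letter for subjects already considered lost, so checking the box could as well start that effort as end it.

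The scope of Section 5.4.1 is also open. It sits under discontinuation of individual subjects, speaks of final status, and does not expressly name the 70-day call or Week 56 completers. However, it follows the description of that call in the same section and uses the same term, so the link is reasonable for discontinuers. For completers it is unsettled.

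The call is not the only route for events. Section 6.1.4 also collects spontaneous reports, and serious events are reportable within 24 hours of site awareness. Section 11.0 promises full source verification, which may show further attempts recorded at the site. These facts reduce the likely loss but do not remove the mismatch.

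A reader might also infer that an unreached subject is recorded as having had no events. The form does not do that, because No Events Reported is a separate box. The narrower point that survives is that the planned tables do not carry the distinction forward.

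**Conclusion.** The mismatch is real and stands in current text: the form is one call and one letter below the Section 5.4.1 minimum. The consequence is plausible but cannot be sized. Adverse events in the last 8 to 10 weeks of the window could go unobserved in subjects closed after one attempt. The documents give no contact rate, loss rate or late-window event rate from which to estimate how many.

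A reader might infer a bias between arms. The documents do not support that: the same form and rule apply to both blinded arms, and nothing shows that failed contacts would differ between them. Nor does the 70-day window apply to everyone in the Induction comparison; it applies only to subjects who enter neither Maintenance nor the extension.

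The conclusion rests on one reading, that the Section 5.4.1 minimum is meant to govern the 70-day call. That is likely for discontinuers and unstated for completers. The point is minor, but more than editorial, because the form guides what sites do at the last scheduled safety contact.

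**What to change.** Reconcile the two texts:

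- Reword the Lost to Follow-up box in Appendix J so that it matches the Section 5.4.1 minimum and cites that section, and add fields for the date of each attempt and of the letter.
- State in Section 5.4.1 or 6.1.4 whether that minimum also governs the 70-day call for Week 56 completers.
- In the safety reporting, show by arm the number of subjects due a 70-day contact for whom it was not completed.

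The cost is a change of form wording, one added table row and, if completers are included, possibly one more call and a letter for each completer who is not reached. For discontinuers it adds no contact effort beyond what Section 5.4.1 already asks.
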